24.1.1 ADDITIONAL SURGERY LIST

A list with additional surgeries collected and its characteristics will be shown.

24.2 ADVERSE EVENTS

The categorical variables to be described are, N and (%) and Clopper-Pearson confidence intervals will be shown at 95.0% as well:

- Patients with at least one adverse event
- Patients with at least one serious adverse event
- Patients with at least one related adverse event (considering related as Possible, Probable and Casual relationship)
- Patients with at least one adverse event which require additional surgery

24.2.1 ADVERSE EVENTS DESCRIPTION

The categorical variables to be described are, N and (%):

- Adverse Event Description by patient
 - If "Unanticipated/Other adverse event" is selected, the following question: "To which macro group do the adverse event belong?", will be shown by patient.

24.2.2 RELATED ADVERSE EVENTS

The categorical variables to be described are, N and (%):

- Adverse Event Description for each: Not related / Possible / Probable / Casual relationship

24.2.1 ADDITIONAL SURGERY ADVERSE EVENTS

For each Adverse Event, the categorical variables to be described are, N and (%):

- Did the adverse event require an additional surgery? YES / NO

- If NO, Could the device deficiency have led to an additional surgery? YES / NO
- Adverse Event Description for each: Require additional surgery / No require additional surgery

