13.1.2.2 Safety Variables

The safety profile of CHIMAERA™ will be assessed through the percentage of patients that required a reoperation (i.e., additional surgery) caused by at least one of the following safety events:

- Expected or unexpected adverse effect potentially or certainly related to the CHIMAERA™ (Adverse Device Effects (ADEs)/Serious Adverse Device Effects (SADEs)) since the nail application until 6 months follow-up after nail implant.
- Medical Device Deficiency (MDDs) (i.e., breaking, loosening, or bending of the nail or of the screws) that caused an effect on the patient since the nail application until 6 months follow-up after nail implant.

All the reoperations that have occurred are considered but also those that have not occurred but that could have occurred (e.g., a patient who had a cut out but for any reasons has not been operated). It should be considered also all ADE/SADE/MDD that could have caused an additional operation.

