13.1.3.2 Evaluation of Safety

The evaluation of safety will be performed through the analysis of the secondary objective of the study: to evaluate the safety profile of the long variant of the CHIMAERA™ used in adult patients according to the manufacturer IFU in routine clinical practice from the time of surgery until 6 months follow-up after nail implant.

The safety analysis will be performed in the “safety population” which includes all patients who have undergone an intramedullary nailing technique with the CHIMAERA™ medical device.

The number and percentage of patients that required a reoperation due to at least one ADE/SADE/MDD will be calculated with a 95% confidence interval (CI). An analysis will be carried out according to degree of severity, seriousness, and relationship with the medical device.

All the reoperations that have occurred are considered but also those that have not occurred but that could have occurred (e.g., a patient who had a cut out but for any reasons has not been operated). It should be considered also all ADE/SADE/MDD that could have caused an additional operation. Therefore, the number and percentage of patients that hypothetically would have caused a reoperation due to at least one safety event will be described and calculated with a 95% CI.

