24.3.3 DEVICE DEFICIENCIES (DD) REQUIRE AN ADDITIONAL SURGERY

For each DD, the categorical variables to be described are, N and (%):

- Did the device deficiency require an additional surgery? YES / NO
 - IF YES, Could surgery be completed with the device in question? YES / NO / Not applicable

- Was a replacement device immediately available to complete surgery?
YES / NO
- did the event lead to a clinically relevant increase in the duration of the surgical procedure? YES / NO
- Is a copy of the operative reports available for the medical evaluation?
YES / NO (
- IF NO, Could the device deficiency have led to an additional surgery? YES / NO
/ Not applicable
- Are x-ray of the deficiency device available? YES / NO / Not applicable
- Are any other patient's clinical evaluation related to the event (i.e labs results, autopsy etc.) available? YES / NO

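### The SAP's adverse-event item on possible surgery names the device deficiency, and no patient-level count of hypothetical reoperations is planned

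*SAP*

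**What the plan says.** Protocol 13.1.2.2 defines the safety endpoint through reoperations caused by an adverse device effect (ADE or SADE) or a medical device deficiency (MDD) up to 6 months. It includes operations that did not happen but could have, with the example "a patient who had a cut out but for any reasons has not been operated". It then widens the scope: "It should be considered also all ADE/SADE/MDD that could have caused an additional operation". Protocol 13.1.3.2 turns this into a required output, with a 95% confidence interval: "the number and percentage of patients that hypothetically would have caused a reoperation due to at least one safety event".

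The SAP's counterpart for adverse events is 24.2.1, Additional Surgery Adverse Events (the number 24.2.1 is used twice in the SAP; this is the second use). Its lead-in is "For each Adverse Event, the categorical variables to be described are, N and" a percentage. The first item is "Did the adverse event require an additional surgery? YES / NO". The follow-up is "If NO, Could the device deficiency have led to an additional surgery? YES / NO".

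The section on deficiencies, SAP 24.3.3, has almost the same follow-up, in its natural place: "IF NO, Could the device deficiency have led to an additional surgery? YES / NO", there with a third, not-applicable option.

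The patient-level adverse-event summary with a confidence interval is in SAP 24.2. It covers patients whose adverse event did require additional surgery.

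**The concern.** The first item in SAP 24.2.1 is about the adverse event; the follow-up switches to the device deficiency. It looks like a carry-over from 24.3.3. Of the variables in SAP section 24, it is the only one that could mark an unoperated ADE or SADE as a hypothetical reoperation.

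If the words are applied as printed, an infection or a non-union without any fault in the implant offers no deficiency to judge. The respondent must answer no, leave it blank, or decide that the item means something else. Two sites could choose differently, and the output would not show which reading was used. A wrong no or a blank would lower the hypothetical count, which makes the device look safer.

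The second part concerns reporting. Even a perfectly recorded item feeds only an event-level table, whereas the protocol asks for a proportion of patients with an interval.

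**Working it through.** This is mainly a comparison of texts; the plan states no figure to reproduce.

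**Step 1: where the hypothetical judgement is made.** Within SAP section 24, the question whether something could have led to surgery appears twice:
- 24.2.1 (Additional Surgery Adverse Events): reported per adverse event, but worded for a deficiency, with yes/no only.
- 24.3.3: reported per deficiency, worded for a deficiency, with yes/no/not applicable.

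The protocol needs the judgement for ADEs and SADEs as well as MDDs. The deficiency side is covered. The adverse-event side rests on the first item alone.

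**Step 2: can an adverse event exist without a deficiency?** Yes. Protocol 10.1 lists infection and non-union among the registered adverse effects. Protocol 13.1.2.2 describes the endpoint deficiencies as breakage, loosening or bending of nail or screws. Cut-out is named in neither list, so the documents leave open whether it is recorded as an adverse event, a deficiency or both.

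**Step 3: what reaches a patient-level rate?**
- SAP 24.1.1: patients with additional surgery, including by reason. Actual surgery only.
- SAP 24.2: patients with an adverse event requiring surgery. Actual need only.
- SAP 24.3: patients with at least one deficiency, whether or not surgery was in question.
- The two follow-up items in 24.2.1 and 24.3.3: counts and percentages per event, with no interval.

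None of these is the hypothetical patient count with a 95% interval that protocol 13.1.3.2 requires.

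**Step 4: scale, as an illustration.** Assumption: all 44 planned patients (SAP section 9) are in the safety population. The effect of one patient is 1/44 = 0.0227, or about 2.3 percentage points. Exact Clopper-Pearson 95% limits (the SAP's method, section 14) are the beta quantiles: lower = Beta(0.025; x, 44 − x + 1), upper = Beta(0.975; x + 1, 44 − x), with lower = 0 when x = 0.

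| Patients x | x/44 | 95% CI |
|---|---|---|
| 0 | 0.0% | 0.0 to 8.0% |
| 1 | 2.3% | 0.1 to 12.0% |
| 2 | 4.5% | 0.6 to 15.5% |
| 3 | 6.8% | 1.4 to 18.7% |

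For context, the literature average for reoperations due to ADEs/SADEs in protocol 6.1 is 5.9%, and 0.059 × 44 = 2.6 patients. With expected counts this small, one patient matters. The documents do not say how many hypothetical reoperations to expect, so the rows show sensitivity and are not a forecast.

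**The case against.** The best case against has four parts.

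**Context.** The item sits under an adverse-event heading, is reported per adverse event, and follows a question about the adverse event. Most readers would take it to mean the adverse event. That is a fair reading, but it requires overriding the printed words, and a plan should not depend on that.

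**The eCRF governs what is collected.** The SAP names an eCRF version (section 3) and the form is a separate attachment. If the form says adverse event, no data are affected and the SAP has only a wording slip. This stands, and it is why the consequence is stated conditionally.

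**Unoperated events stay visible.** SAP 24.2.1 tabulates adverse-event descriptions by whether surgery was required, and 24.2.3 lists every adverse event. Protocol 12.1 also defines deficiencies broadly, so a cut-out might be recorded as one and reach the correctly worded item in 24.3.3. This also stands. A reader might infer that unoperated cut-outs are lost, or that every unoperated device-related event without a deficiency is missed. The documents do not support that: such events can still be found, and what may be missing is a valid judgement on whether they could have led to surgery.

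**No planned rate uses the item.** Correct: the wording change alone would alter no planned patient-level percentage or interval. This shows that the protocol's required summary is absent from the SAP, and that the two corrections belong together. A summary added without correcting the item would inherit the ambiguous input.

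**Conclusion.** The point holds in two linked parts. First, the follow-up item in SAP 24.2.1 names the wrong kind of event, so hypothetical reoperations due to ADEs/SADEs may not be reliably identified. An actual loss of data is not shown; it depends on the eCRF label and on how a cut-out is recorded, and neither can be settled from the protocol and SAP. Second, the SAP omits the patient-level hypothetical count with a 95% interval that protocol 13.1.3.2 requires. This part does not depend on the eCRF.

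If 44 patients form the safety population, each misclassified patient shifts the rate by about 2.3 points; moving from none to one raises the upper limit from 8.0% to 12.0%. The number 44 is a planned maximum, and the number of patients affected is unknown. The correction should be made before data extraction, because it concerns an input to the safety endpoint and costs very little.

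**What to change.** 1. In SAP 24.2.1 (Additional Surgery Adverse Events), replace *device deficiency* with *adverse event* in the follow-up item and leave the rest as it is.
2. Check the adverse-event page of the eCRF. If it has the same wording, correct the label before extraction. If collection has already begun under that label, query the sites on unoperated adverse events through the clarification process in protocol 15.7.2.
3. Add a safety-population summary to SAP section 24: patients with at least one ADE, SADE or MDD up to 6 months that required, or could have required, additional surgery, with number, percentage and Clopper-Pearson 95% interval. Derive the hypothetical part from the corrected 24.2.1 item (for ADEs/SADEs) together with the 24.3.3 item (for deficiencies), count each patient once, and show actual and hypothetical reoperations separately.

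The cost is one phrase and one table in the SAP and, if needed, one form label. No extra patients or new assessments are required.

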24.2.2 ADVERSE EVENTS SERIOUSNESS

For each Adverse Event, the categorical variables to be described are, N and (%):

- Adverse Event Description: Seriousness / Not seriousness

24.2.3 ADVERSE EVENTS LIST

A list with adverse events collected and its characteristics will be shown.

24.3 DEVICE DEFICIENCIES (DD)

The categorical variables to be described are, N and (%) and Clopper-Pearson confidence intervals will be shown at 95.0% as well:

- Patients with at least one DD

24.3.1 DEVICE DEFICIENCIES (DD) TYPES AND DESCRIPTION

The categorical variables to be described are, N and (%):

- Deficiency description by patient

24.3.2 DEVICE DEFICIENCIES (DD) RESULTED IN AN ADVERSE EVENT FOR THE PATIENT

For each DD, the categorical variables to be described are, N and (%):

- Did this DD resulted in an Adverse Event for the patient? by patient YES / NO, If the answer is YES
 - Are any other patient's clinical evaluation related to the event (i.e. labs results, autopsy etc.) available? YES / NO
 - Is it an expected Device Deficiency (listed in the IFU of the product)? YES / NO, if NO the macro group will be described.

24.3.3 DEVICE DEFICIENCIES (DD) REQUIRE AN ADDITIONAL SURGERY

For each DD, the categorical variables to be described are, N and (%):

- Did the device deficiency require an additional surgery? YES / NO
 - IF YES, Could surgery be completed with the device in question? YES / NO / Not applicable

- Was a replacement device immediately available to complete surgery?
YES / NO
- did the event lead to a clinically relevant increase in the duration of the surgical procedure? YES / NO
- Is a copy of the operative reports available for the medical evaluation?
YES / NO (
- IF NO, Could the device deficiency have led to an additional surgery? YES / NO
/ Not applicable
- Are x-ray of the deficiency device available? YES / NO / Not applicable
- Are any other patient's clinical evaluation related to the event (i.e labs results, autopsy etc.) available? YES / NO

24.3.4 DEVICE DEFICIENCIES (DD) LIST

A list with DD collected and its characteristics will be shown.
